The results of the labs drawn on Week 1 Day 1 need to be reviewed prior to dosing **IF** an additional lab draw within 72 hours of the initial dose at Week 1 Day 1 was not drawn **AND** reviewed.

Prior to Each Subsequent Dose Increase, for all Subjects:

- Within 72 hours of each subsequent dose increase: The chemistry/hematology panel should be repeated. The results should be reviewed prior to dose increasing.
- Prior to dosing, on the day of each subsequent dose increase: Before dosing, the chemistry/hematology panel should be drawn. The results of the labs drawn on Day 1 of each dose increase need to be reviewed prior to dosing **IF** an additional lab draw within 72 hours of the dose increase was not drawn **AND** reviewed.

POST-DOSE LABS:

For all subjects, the chemistry/hematology panel (refer to [Table 4](#), Clinical Laboratory Tests) should be monitored at 6 to 8 hours and at 24 hours after the first dose of venetoclax (20 mg) and after the first dose increase (50 mg). Electrolyte abnormalities should be corrected promptly. The next venetoclax doses (the Day 2 20 mg venetoclax dose and the Day 2 50 mg venetoclax dose) should not be administered until the 24 hour lab results have been evaluated. Electrolyte abnormalities should be corrected promptly. For subjects who continue to be at risk of TLS, the same lab monitoring schedule (i.e., 6 to 8 hour and 24-hr post dose) should be followed at the subsequent dose increases.

This monitoring is also recommended during the re-initiation of the therapy after a dose interruption.

Additional monitoring may be required based on the risk assessment by the investigator and as directed by the AbbVie TA MD.

Local laboratories will be utilized to process and provide results for clinical laboratory tests allowing for immediate subject medical management. The principal investigator or sub-investigator will review, initial, and date all laboratory results used for subject treatment management after receipt from the local laboratory. Local laboratory values will be entered by the site directly onto the appropriate eCRF and laboratory normal ranges for the laboratory that is used will be provided to the AbbVie Clinical Team.

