6.1.1 Definitions

6.1.1.1 Adverse Event

An adverse event (AE) is defined as any untoward medical occurrence in a subject or clinical investigation subject administered a pharmaceutical product and which does not necessarily have a causal relationship with this treatment. An adverse event can therefore be any unfavorable and unintended sign (including an abnormal laboratory finding), symptom, or disease temporally associated with the use of a medicinal (investigational) product, whether or not the event is considered causally related to the use of the product.

Such an event can result from use of the drug as stipulated in the protocol or labeling, as well as from accidental or intentional overdose, drug abuse, or drug withdrawal. Any worsening of a pre-existing condition or illness is considered an adverse event.

Worsening in severity of a reported adverse event should be reported as a new adverse event. Laboratory abnormalities and changes in vital signs are considered to be adverse events only if they result in discontinuation from the study, necessitate therapeutic medical intervention, meets protocol specific criteria (see Section 6.1.8 Toxicity Management) or if the investigator considers them to be adverse events.

For this protocol, disease progression is an efficacy endpoint. These data will be captured as efficacy assessment data only. Thus, events that are clearly consistent with the expected pattern of progression of the underlying disease (such as transformation to more aggressive histology) will result in discontinuation from the study and should not be recorded as adverse events but reported on the Study Completion eCRF. However, if a subject experiences an adverse event (e.g., pneumonia, pyrexia, fatigue, etc.) and is also found to have disease progression, report the adverse event. If there is any uncertainty as to whether an event is due to disease progression, it should be reported as an adverse event.

An elective surgery/procedure scheduled to occur during a study will not be considered an adverse event if the surgery/procedure is being performed for a pre-existing condition and the surgery/procedure has been pre-planned prior to study entry. However, if the pre-existing condition deteriorates unexpectedly during the study (e.g., surgery performed earlier than planned), then the deterioration of the condition for which the elective surgery/procedure is being done, will be considered an adverse event.

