Appendix G. Definitions of Laboratory and Clinical Tumor Lysis Syndrome

Metabolic Abnormality	Criteria for Classification of Laboratory Tumor Lysis Syndrome	Criteria for Classification of Clinical Tumor Lysis Syndrome
Hyperruricemia	Uric acid > 8.0 mg/dL (475.8 µmol/liter) in adults or above the upper limit of the normal range for age in children	
Hyperphosphatemia	Phosphorus > 4.5 mg/dL (1.5 mmol/liter) in adults or > 6.5 mg/dL (2.1 mmol/liter) in children	
Hyperkalemia	Potassium > 6.0 mmol/liter	Cardiac dysrhythmia or sudden death probably or definitely caused by hyperkalemia
Hypocalcemia	Corrected calcium < 7.0 mg/dL (1.75 mmol/liter) or ionized calcium < 1.12 (0.3 mmol/liter) [†]	Cardiac dysrhythmia, sudden death, seizure, neuromuscular irritability (tetany, paresthesias, muscle twitching, carpopedal spasm, Trousseau's sign, Chvostek's sign, laryngospasm, or bronchospasm), hypotension, or heart failure probably or definitely caused by hypocalcemia
Acute kidney injury [‡]	Not applicable	Increase in the serum creatinine level of 0.3 mg/dL (26.5 µmol/liter) (or a single value > 1.5 times the upper limit of the age-appropriate normal range if no baseline creatinine measurement is available) or the presence of oliguria, defined as an average urine output < 0.5 mL/kg/hr for 6 hrs

[†] The corrected calcium level in milligrams per deciliter = measured calcium level in milligrams per deciliter + 0.8 × (4-albumin in grams per deciliter).

[‡] Acute kidney injury is defined as an increase in the creatinine level of at least 0.3 mg per deciliter (26.5 µmol per liter) or a period of oliguria lasting 6 hours or more. By definition, if acute kidney injury is present, the subject has clinical tumor lysis syndrome. Data about acute kidney injury from Levin et al.

Note: In laboratory tumor lysis syndrome, two or more metabolic abnormalities must be present during the same 24-hour period within 3 days before the start of therapy or up to 7 afterward. Clinical tumor lysis syndrome requires the presence of laboratory tumor lysis syndrome plus an increased creatinine level, seizures, cardiac dysrhythmia, or death.

Appendix H. Recommendations for Initial Management of Electrolyte Abnormalities and Prevention of Tumor Lysis Syndrome (TLS)

Section 1: First Dose of Venetoclax or Dose Escalation

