11.2 Analysis of Treatment-Emergent Adverse Events

All summaries/analyses involving AEs will include treatment-emergent adverse events (TEAE) only, unless otherwise specified. TEAE are defined as any event with onset after the first dose of venetoclax and no more than 30 days after the last dose of venetoclax. Events where the onset date is the same as the venetoclax start date are assumed to be treatment-emergent, unless the venetoclax start time and the AE start time are collected and the AE start time is prior to the venetoclax start time. If an incomplete onset date was collected for an AE, the AE will be assumed to be treatment-emergent unless there is evidence that confirms that the AE was not treatment-emergent (e.g., the AE end date was prior to the date of the first dose of venetoclax).

Treatment-emergent adverse events will be summarized by maximum severity grade level of each preferred term. Each adverse event will be assigned a grade level (grade 1, 2, 3, 4, or 5) by the investigator. If a subject has an AE with unknown severity, then the subject will be counted in the severity grade level category of "unknown," even if the subject has another occurrence of the same event with a severity present. The only exception is if the subject has another occurrence of the same AE with the highest grade level (grade 5). In this case, the subject will be counted under the "Grade 5" category.

Treatment-emergent adverse events will be summarized by relationship of each preferred term to venetoclax, as assessed by the investigator. If a subject has an adverse event with

unknown relationship, then the subject will be counted in the relationship category of "unknown," even if the subject has another occurrence of the same event with a relationship present. The only exception is if the subject has another occurrence of the same adverse event with a relationship assessment of "Reasonable Possibility." In this case, the subject will be counted under the "Reasonable Possibility" category.

Adverse events will be coded using the Medical Dictionary for Regulatory Activities (MedDRA). The actual version of the MedDRA coding dictionary will be noted in the clinical study report.

Adverse event data will be summarized and presented using primary MedDRA system organ classes (SOCs) and preferred terms (PTs) according to the MedDRA coding dictionary version 20.1 or higher.

Adverse Event

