An overview of AEs will be presented consisting of the number and percentage of subjects experiencing at least one event for each of the following AE categories:

- Any treatment-emergent adverse event;
- Any treatment-emergent adverse event with reasonable possibility related to venetoclax by the investigator;
- Any treatment-emergent NCI toxicity (CTCAE V4.03) grade 3, 4, or 5 adverse events;
- Any treatment-emergent NCI toxicity (CTCAE V4.03) grade 3 or 4 adverse event;
- Adverse events broken down by NCI toxicity grade (Severity);
- Any treatment-emergent serious adverse event;
- Any treatment-emergent adverse event leading to discontinuation of venetoclax;
- Any treatment-emergent adverse event leading to venetoclax interruption
- Any treatment-emergent adverse event leading to venetoclax reduction

- Any treatment-emergent adverse event leading to death;

For summary tables of AE by PT, subjects reporting more than one AE for a given PT will be counted only once for that term (most severe/highest grade incident for the severity tables and most related incident for the relationship tables). Subjects reporting more than one AE within an SOC will be counted only once for that SOC. Subjects reporting more than one AE will be counted only once in the overall total.

Adverse Events of Special Interest

Adverse events of special interest will be summarized. The list of adverse events of special interest is shown in [Table 3](#).

For each of the adverse event of interest, the number and percentage of subjects experiencing at least one treatment-emergent adverse event will be presented overall and by SOC and PT. In addition, a listing of treatment-emergent adverse events for subjects meeting each of the search criteria will be provided.

Table 3. Adverse Events of Special Interest

Risk	Search Criteria
Tumor Lysis Syndrome (three searches)	
 1) SMQ – "Tumour lysis syndrome" (Narrow-scope) 2) SMQ – "Tumour lysis syndrome" (Narrow) plus PT terms of "Hyperkalaemia," "Hyperuricaemia," "Hyperphosphataemia," "Hypocalaemia," "Blood potassium increased," "Blood uric acid increased," "Blood phosphorus increased," "Blood calcium decreased" 3) SMQ – "Tumour lysis syndrome" (Narrow) plus broad-scope terms with algorithm applied (i.e., two events from category B and one event from category C required for a subject to be counted as having a TLS event)

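### TLS is identified from adverse-event terms only; a supplementary derivation on the protocol's Appendix G laboratory definition would use chemistry already collected

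*SAP*

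**What the plan says.** **SAP 11.2, Table 3.** There are three TLS searches:
- Search 1 is the narrow standardised MedDRA query (SMQ) for TLS.
- Search 2 is the narrow SMQ plus eight electrolyte preferred terms, one of them printed as "Hypocalaemia".
- Search 3 is the narrow SMQ plus broad-scope terms under an algorithm: "two events from category B and one event from category C required for a subject to be counted as having a TLS event". A narrow term alone still qualifies.

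For each search, "the number and percentage of subjects experiencing at least one treatment-emergent adverse event will be presented overall and by SOC and PT", with a listing of events for the subjects found. No search states an interval between events. The only time limit is the treatment-emergent window, from first dose to "no more than 30 days after the last dose of venetoclax".

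**Protocol Appendix G.** For laboratory TLS, "two or more metabolic abnormalities must be present during the same 24-hour period", from 3 days before the start of therapy to 7 days after. Each abnormality has a numeric cut-off. Clinical TLS is laboratory TLS plus a raised creatinine, seizure, dysrhythmia or death.

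**Data collected.** Under protocol 5.3.1.1 all subjects have chemistry at 6 to 8 hours and at 24 hours after the 20 mg start and after the step to 50 mg. Subjects still at risk have the same draws at later steps. Sites enter local values on the eCRF.

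**Laboratory analysis.** SAP 11.4 names potassium, calcium, inorganic phosphorus, uric acid, creatinine and albumin. For these, SAP 11.4.1 plans CTCAE shift tables, one variable at a time, and grade 3 to 4 listings. For potential drug-induced liver injury (DILI) it also derives a laboratory signal with a 72-hour link. There is no laboratory derivation for TLS.

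**The concern.** TLS is one of the two identified risks in protocol 6.1.1.4, and it is the reason for the 5-week titration. The protocol's introduction reports earlier experience as clinical TLS and laboratory TLS separately. The planned output yields neither figure on the Appendix G definition. What it yields depends on whether an investigator recorded an AE and which term was chosen. Cases could be missed at that step, and electrolyte events unrelated to tumour lysis could enter the broadest search. A reader of the study report could not tell how far either has happened.

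**Working it through.** The plan states no TLS rate or TLS precision, so there is no figure to reproduce. The check is mainly textual, with illustrative arithmetic on stated assumptions.

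**1. Definitions side by side**

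| | SAP Table 3 | Protocol Appendix G |
|---|---|---|
| Source | AE terms | Laboratory values, plus clinical event for clinical TLS |
| Threshold | None; a term was reported | Numeric, by analyte |
| Time link | None | Same 24 hours |
| Outer window | First dose to last dose + 30 days | Day −3 to +7 around start of therapy |

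**2. Can the planned laboratory output stand in?** No. A shift table shows each analyte's worst grade separately. A subject whose phosphorus peaks in Week 1 and whose uric acid peaks at Week 40 fills the same cells as one in whom both peak on the same day. The listings show individual values, but only at grade 3 to 4, and no co-occurrence rule is applied to them.

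**3. Does every Appendix G case become an AE?** Not by rule. Protocol 6.1.1.1 begins: "Laboratory abnormalities and changes in vital signs are considered to be adverse events only if they result in discontinuation from the study". It adds three further routes: need for therapeutic intervention, meeting the criteria in 6.1.8, or the investigator's judgement. Table 7 in 6.1.8.2 does cover chemistry changes pointing to TLS, but gives no cut-offs.

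Appendix H does not close the gap. Take a dose increase after the first dose, phosphorus between 4.5 and 5.0 mg/dL, and corrected calcium below 7.0 mg/dL without symptoms. Both values meet Appendix G (above 4.5; below 7.0). Neither meets its Appendix H row, because phosphorus there needs at least 5.0 with a rise and calcium needs symptoms. Whether an AE is recorded then rests on the investigator. This compares definitions for counting; it is no comment on management.

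**4. If the case is recorded as two electrolyte AEs, where does it appear?** Search 2 adds the electrolyte terms to the narrow SMQ, which implies that the narrow SMQ does not hold them, so search 1 misses the case. Search 3 needs three events, so two cannot satisfy it. With three or more electrolyte AEs the answer depends on what categories B and C contain, which the documents do not list. The two-abnormality case therefore appears only in search 2.

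**5. What else is in search 2?** Any single electrolyte AE in the window. With the last dose at Week 108 (nominal day 750 in SAP Table 2):
- Window = 750 + 30 = 780 days; titration = 35 days; 35/780 = 4.5%.
- With the last dose at Week 48 (day 330): 35/(330 + 30) = 9.7%.

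These are shares of calendar time, not of events.

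**6. Chance counts.** Assume 250 subjects and Poisson numbers of unrelated events: mean *b* electrolyte AEs and mean *c* category C AEs per subject, with electrolyte terms treated as category B.
- Search 2: 250 × (1 − e^−b)
- Search 3, no time link: 250 × [1 − e^−b(1 + b)] × (1 − e^−c)

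| b | c | Search 2 | Search 3 |
|---|---|---|---|
| 0.1 | 0.02 | 23.8 | 0.02 |
| 0.3 | 0.05 | 64.8 | 0.45 |
| 0.6 | 0.1 | 112.8 | 2.9 |

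Unrelated events therefore accumulate in search 2. The missing time link in search 3 adds few.

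**7. Possible loss.** If a share L of 250 subjects meets laboratory TLS and a fraction f of those is recorded as AEs, 250 × L × f are found. For L = 5% (12.5 subjects), f = 25%, 50%, 75% and 100% gives 3.1, 6.3, 9.4 and 12.5. For L = 2% (5 subjects) the same range of f gives 1.25 to 5; for L = 10% (25 subjects), 6.25 to 25. The loss runs from three quarters to none, and the documents do not fix L or f.

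**8. Spelling.** "Hypocalaemia" is evidently meant as hypocalcaemia, since the same list has the matching term for a low blood calcium. A literal string match would miss it. The effect is confined to search 2 and lowers its count.

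**The case against.** The best defence is that Table 3 offers three tiers of breadth and does not call search 2 the TLS rate. Results by preferred term and the listings let a reader separate isolated hyperkalaemia from TLS. Search 1 is untouched by the time-link and spelling points. Sections 6.1.1.1 and 6.1.8 send many TLS-type changes to AE reporting, and 6.1.1.2 allows post-dose TLS laboratories that need intervention to count towards seriousness. Chemistry is drawn most often in titration, so detection is front-loaded, and TLS risk is reassessed after later dose interruptions, so late events are not all irrelevant. The DILI search in Table 3 has no time link either, so the AE searches are consistent with one another. Neither document promises Appendix G as an analysis definition.

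All of this stands, and it makes the point a gap in the analysis rather than a breach of the plan. Two things survive it. Tables and listings of AEs cannot show a case that was never recorded as one. And the consistency argument favours the change: DILI has an AE search and a time-linked laboratory rule, while TLS has only the AE searches.

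**Conclusion.** TLS may be misclassified in two ways: laboratory TLS that goes unrecorded or is visible only in search 2, and isolated electrolyte events mixed into search 2. The size of neither can be derived from the documents; the figures above rest on assumed rates and show only where each effect would fall.

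A reader might infer more, and the documents do not support it:
- *That the reported TLS incidence will be wrong in both directions.* No TLS rate is given, and the reporting rules may capture most or all cases.
- *That search 3 inflates the count because its events need not coincide.* Its three-event rule admits few chance cases (about 0.02 to 2.9 of 250 on the assumed rates).
- *That some 95% of counted events fall outside the risk period.* That is a share of time for a Week 108 completer.
- *That the misspelling distorts TLS counts generally.* It touches one term of one search, only under literal matching, and may be an artefact of reading the PDF.

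This is a low-cost improvement to the measurement of an identified risk. It does not affect the efficacy conclusions.

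**What to change.** 1. **SAP 11.4.1, beside the DILI rule:** derive laboratory TLS as two or more Appendix G abnormalities within the same 24 hours. Corrected calcium can be computed from the collected calcium and albumin. Derive clinical TLS by adding the Appendix G creatinine criterion from chemistry, and seizure, dysrhythmia or death from the AE and death data.
2. **State the window as an analysis definition.** Appendix G anchors it to the start of therapy. Apply it after the first dose and after each dose increase. Steps are 7 days apart, so the 3 days before one step overlap the 7 days after the previous one; assign such cases to the dose being taken. If the eCRF holds dates without times, say how 24 hours is approximated.
3. **Report both by dose level,** with the number of subjects who had post-dose chemistry at that level as denominator, since later post-dose draws are made only in those still at risk. Present this as a supplement to the three AE searches.
4. **Table 3:** tabulate search 2 by onset in titration or re-titration versus later, and correct the calcium term to hypocalcaemia if the error is in the source. A stated interval for search 3 is optional and secondary.

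The cost is one laboratory derivation, a written window choice and one date split in programming. No new data are needed.

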subjects are included in overall pooled analyses for reporting Reference Safety Information. The 2473 subjects in the overall pooled analysis include 2224 oncology subjects (987 in monotherapy studies and 1237 in combination therapy studies), 153 healthy volunteers, 23 subjects with hepatic impairment and 73 subjects with SLE. Of the 2224 oncology subjects, 1132 subjects had CLL/small lymphocytic lymphoma (SLL), 569 subjects had Non-Hodgkin's Lymphoma (NHL), 172 subjects had multiple myeloma (MM), 340 had Acute Myeloid Leukemia (AML), and 11 subjects had myelodysplastic syndrome (MDS). 787 subjects with blinded data have been treated with either venetoclax combination therapy or a comparator treatment in company-sponsored venetoclax oncology studies. Doses administered in venetoclax clinical studies have ranged from 20 mg to 1200 mg.

The most common adverse events reported in venetoclax monotherapy studies were neutropenia (39.3%), nausea (31.4%) and diarrhea (24.9%). The most common adverse events that were grade 3 and above were neutropenia (34.9%), anemia (13.8%) and thrombocytopenia (12.8%). The most common serious adverse events were febrile neutropenia (6.1%), pneumonia (5.4%), malignant neoplasm progression (3.4%), and pyrexia (3.3%).

Tumor lysis syndrome (TLS) is an important risk, particularly in subjects with R/R CLL. As a result of on-target effects, the potential for TLS with venetoclax was identified early in the program when the initial 3 subjects with CLL/SLL received starting doses of 100 mg or 200 mg and experienced TLS, which was reported as an adverse event for each. Subsequently, 2 fatal events in the setting of TLS and another event of clinical TLS in subjects with CLL/SLL occurred in December 2012. After comprehensive review of all safety data available from studies with venetoclax, a revised dosing regimen with a dose-titration phase of 5 weeks and enhanced TLS prophylaxis and monitoring measures were implemented in all CLL studies. A subsequent analysis of data from subjects with CLL/SLL following the implementation of prophylaxis measures, who completed monotherapy indicated a marked reduction in severity and frequency of TLS when compared to the previous analysis. None of the subjects experienced any serious

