Appendix I. Adverse Events Commonly Associated with CLL Study Population and/or Progression of CLL

Disease-Related Events – CLL

Lymphadenopathy
Splenomegaly
Hepatomegaly
Leukemia cutis (macules, papules, plaques, nodules, ulcers, or blisters) Lymphocytosis
Cytopenias (neutropenia, anemia and thrombocytopenia)
Febrile neutropenia
Autoimmune hemolytic anemia
Autoimmune thrombocytopenia
Hypogammaglobulinemia
Infections (bacterial, viral, and fungal)
Second primary cancers, all types Fatigue
Unexplained weight loss
Pyrexia
Bruising
Minor hemorrhages
Pain, all types
Malignant neoplasm progression, including death

Population-Related Comorbidities

Hypertension
Rheumatoid arthritis/osteoarthritis
Hyperlipidemia
Peptic ulcer
Inflammatory bowel disease

Coronary artery disease
Peripheral vascular disease
Cardiomyopathy
Valvular disease
Atrial fibrillation
Diabetes mellitus
Chronic obstructive pulmonary disease
Cerebrovascular accident
Transient ischemia attack

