Neutropenia	PT terms – "Neutropenia," "Neutrophil count decreased," "Febrile neutropenia," "Agranulocytosis," "Neutropenic infection," and "Neutropenic sepsis"
Serious Infection, Including Opportunistic Infections	SAEs in the SOC of "Infections and Infestations"
Second Primary Malignancy	SMQ – "Malignant tumours" (Narrow) and "Myelodysplastic syndromes" (Narrow)
Lymphopenia	PT terms – "Lymphopenia" and "Lymphocyte count decreased"
Anemia	PT terms – "Anaemia" and "Haemoglobin decreased"
Thrombocytopenia	PT terms – "Thrombocytopenia" and "Platelet count decreased"
Drug Induced Liver Injury (DILI)	SMQ – "Drug related hepatic disorders – comprehensive search"
Medication Error	SMQ – "Medication error" (broad)

SMQ = Standardised MedDRA Query

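### The second-primary-malignancy search has no exclusion for the study disease, so uncertain CLL progression, or recurrence of an earlier cancer, can enter the headline count as a new cancer

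*SAP*

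**What the plan says.** SAP 11.2, Table 3, defines the risk Second Primary Malignancy by "SMQ – 'Malignant tumours' (Narrow) and 'Myelodysplastic syndromes' (Narrow". For each risk in that table, "the number and percentage of subjects experiencing at least one treatment-emergent adverse event will be presented overall and by SOC and PT". The same section plans an event-level listing of whatever each search picks up. No term is excluded, the medical history is not checked and no adjudication is described, here or elsewhere in the SAP.

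The protocol limits what reaches this search. On disease progression, section 6.1.1.1 says "These data will be captured as efficacy assessment data only". Events clearly fitting progression ("such as transformation to more aggressive histology) will result in discontinuation from the study and should not be recorded as adverse events") go to the Study Completion form instead. Section 6.1.1.2 keeps progression deaths out of the serious adverse events. Section 6.1.1.3 bars unequivocal progression from adverse event reporting, even when fatal. Section 6.1.2.1.1 sends deaths due solely to CLL progression to the Study Completion form only.

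The protocol also leaves a way in. Section 6.1.1.1 adds: "If there is any uncertainty as to whether an event is due to disease progression, it should be reported as an adverse event". Appendix I lists "Malignant neoplasm progression, including death" among the events anticipated in this population, as a separate entry from second primary cancers.

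**The concern.** Every subject enters with a malignancy, so a search on malignancy terms cannot by itself tell a new cancer from the old one. The protocol's Appendix I treats progression and second cancers as different things; the SAP has no rule that keeps them apart once a progression term is on the adverse event form.

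A second route does not depend on the progression rules. Exclusion criterion 4 (protocol 5.2.2) admits subjects whose earlier cancer was confined and treated with curative intent. A recurrence of that cancer during treatment is not a new primary, yet Table 3 would count it if its term is in the query.

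The trial has one arm. The second-malignancy percentage will be read at face value, with no control rate in which the same misclassification would appear. The count is likely to be small, so a few wrongly included subjects can change it noticeably. At stake is one descriptive safety figure, not the primary endpoint.

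**Working it through.** The plan states no figure for second primary malignancy, so there is none to reproduce. The check has two parts.

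**Setting the rules side by side**

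| Event | Protocol rule | Can it reach the Table 3 count? |
|---|---|---|
| Clear CLL progression | Efficacy data only (6.1.1.1); not an adverse event even if fatal (6.1.1.3) | Only if misreported |
| Clear transformation | Named as not to be recorded (6.1.1.1) | Only if misreported |
| Death due solely to CLL | Study Completion form only (6.1.2.1.1) | Only if misreported |
| Death not attributed solely to CLL | Causing or contributing condition goes on the adverse event form (6.1.2.1.1) | Yes, if that condition is coded to a matching term |
| Uncertain progression | Report as an adverse event (6.1.1.1) | Yes, if coded to a matching term |
| Suspected transformation without biopsy | Biopsy is asked for where possible (5.3.3.2); if doubt remains, the uncertainty rule applies | Yes, but less often |
| Recurrence of an earlier cancer | No rule | Yes, if coded to a matching term |

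Exposure is therefore limited to uncertain or misreported disease events and to recurrences. For those, nothing in the SAP takes the event out again.

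**Scale**

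Inputs:
- n = 250 planned subjects (protocol synopsis; SAP 4.2).
- p = the share of subjects with a study-disease event that reaches the adverse event form and matches a query. The documents do not give it. I take 0.5% and 1% as assumptions, and 3.4% as an upper case. The 3.4% is the rate of malignant neoplasm progression as a serious event in venetoclax monotherapy studies (protocol 3.0).
- s = the true second-malignancy rate. The documents do not give it. I assume 5%, with 2% and 10% as a range.

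Formulas: expected additions = n × p. Chance of at least one = 1 − (1 − p)^n. Reported rate, taking the two kinds of event as independent = s + p(1 − s). Share of counted subjects with no new cancer = p(1 − s) / [s + p(1 − s)].

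| p | Expected additions | Chance of at least one | Reported rate if s = 5% | Share with no new cancer if s = 5% |
|---|---|---|---|---|
| 0.5% | 250 × 0.005 = 1.25 | 0.71 | 0.05 + 0.005 × 0.95 = 5.5% | 0.00475 / 0.05475 = 9% |
| 1% | 250 × 0.01 = 2.5 | 0.92 | 0.05 + 0.01 × 0.95 = 6.0% | 0.0095 / 0.0595 = 16% |
| 3.4% | 250 × 0.034 = 8.5 | 0.9998 | 0.05 + 0.034 × 0.95 = 8.2% | 0.0323 / 0.0823 = 39% |

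Over s from 2% to 10% and the same three values of p, the last column runs from 4% (s = 10%, p = 0.5%) to 63% (s = 2%, p = 3.4%). These figures cover study-disease events only. The documents give no basis for sizing recurrences of earlier cancers.

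**The case against.** The strongest reply is that the protocol already handles this. Four sections keep clear progression or progression deaths out of the adverse event data, and one of them names transformation. The sentence on uncertainty directly follows an example of pneumonia, pyrexia or fatigue in a subject who also progresses. Read that way, an uncertain event would usually be entered as a symptom or infection, not as a malignancy. Appendix I mainly serves to define which events count as expected for reporting, and its parent section bars unequivocal progression. Baseline CLL is not itself counted, because only treatment-emergent events are. Finally, the preferred-term table and listing let a reader see a progression term under its own name and subtract it.

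Much of this stands. A reader might infer from Table 3 that CLL progression and transformation will routinely be counted as new cancers, or that about 3.4% of subjects will be added. The documents support neither. Clear cases are kept out, and the 3.4% comes from other studies whose reporting rules are not given, in a programme that also covered lymphoma, myeloma and acute myeloid leukaemia. Nor is the figure made uninterpretable, since the hits stay visible.

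Three things remain. The uncertainty rule is worded for any event, and nothing stops a site from entering a progression term under it. The recurrence route is untouched by these rules. And the listing shows the hits without changing the headline count; deciding after the data are seen which hits to discount is a post hoc choice that the SAP could settle in advance.

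**Conclusion.** The point holds in a limited form. As written, Table 3 can count uncertain CLL progression, less often transformation, and recurrence of an earlier cancer as second primary malignancies. The wording must stay at can, not will.

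The size is unknown: 1 to 3 of 250 subjects if 0.5% to 1% have such an event, and 8 to 9 as an upper case. All of this assumes that the queries contain terms for CLL, its progression or its transformation. That is a reasonable inference from the name Malignant tumours, but the term lists are not in the documents; if no such terms are there, the study-disease effect is nil. The recurrence effect likewise needs a matching term and is not sized.

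The consequence is an overstated headline figure in one of nine descriptive rows. The primary analysis is unaffected. The change is worth making because it is cheap and does no harm if it proves unnecessary.

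**What to change.** Keep both queries in SAP Table 3 as the first-stage search. Add that, after medical review of the listed hits, the Second Primary Malignancy count excludes:

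- preferred terms for CLL/SLL, its progression or its transformation;
- recurrence of a malignancy recorded in the medical history before first dose.

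Show the excluded events in a separate row beneath the count, so that nothing is hidden and a reader can rebuild the unfiltered figure. Fix the rule before the review begins. Table 3 already tailors its tumour lysis searches with added terms and an algorithm, so this fits the style of the plan.

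The cost is a sentence or two of SAP wording, one table row and a short medical review of the listed events. No new data are needed.
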